8.2.3 Expectedness

The PI will be responsible for determining whether an AE is expected or unexpected. An AE will be considered unexpected if the nature, severity, or frequency of the event is not consistent with the risk information previously described for the study device.

8.3 Time Period and Frequency for Event Assessment and Follow-Up

The occurrence of an AE or SAE may come to the attention of study personnel during study visits and interviews of a study participant presenting for medical care, or upon review by one of investigators. All AEs including local and systemic reactions not meeting the criteria for SAEs will be captured on the appropriate eCRF. Information to be collected includes event description, time of onset, clinician's assessment of severity, relationship to study procedure (assessed only by those with the training and authority to make a diagnosis), and time of resolution/stabilization of the event. All AEs occurring while on study must be documented appropriately regardless of relationship. All AEs will be followed to adequate resolution.

Any medical condition that is present at the time that the participant is screened will be considered as baseline and not reported as an AE. However, if the study participant's condition deteriorates at any time during the study, it will be recorded as an AE. UPs will be recorded in the data collection system throughout the study.

CONFIDENTIAL

Changes in the severity of an AE will be documented to allow an assessment of the duration of the event at each level of severity to be performed. AEs characterized as intermittent require documentation of onset and duration of each episode.

The PI will record all reportable events with start dates occurring any time after informed consent is obtained until 7 (for non-serious AEs) or 30 days (for SAEs) after the last day of study participation. At each study visit, the investigator will inquire about the occurrence of AE/SAEs since the last visit. Events will be followed for outcome information until resolution or stabilization.

All unresolved adverse events should be followed by the investigator until the events are resolved, the subject is lost to follow-up, or the adverse event is otherwise explained. At the last scheduled visit, the investigator should instruct each subject to report any subsequent event(s) that the subject, or the subject's personal physician, believes might reasonably be related to participation in this study. The investigator should notify the study sponsor of any death or adverse event occurring at any time after a subject has discontinued or terminated study participation that may reasonably be related to this study. The sponsor should also be notified if the investigator should become aware of the development of cancer or of a congenital anomaly in a subsequently conceived offspring of a subject that has participated in this study.

8.4 Reporting Procedures – Notifying the IRB

8.4.1 Adverse Event Reporting

The principal investigator will promptly notify the IRB of any unanticipated problems involving risks to subjects or others that occurs during the course of a study within **five working days** of learning about the event using Research Navigator.

8.4.2 Serious Adverse Event Reporting

Serious adverse events will be captured from the time of the main study's informed consent through 30 days after the last follow-up visit. The principal investigator will promptly notify the IRB of any unanticipated problems involving risks to subjects or others that occurs during the course of a study within **five working days** of learning about the event using Research Navigator.

The investigators shall submit to the sponsor and to the reviewing IRB a report of any unanticipated adverse device effect occurring during an investigation as soon as possible, but in no event later than 10 working days after the investigator first learns of the effect.

The sponsors who conduct an evaluation of an unanticipated adverse device effect under 812.46(b) shall report the results of such evaluation to FDA and to all reviewing IRB's and participating investigators within 10 working days after the sponsor first receives notice of the effect. Thereafter the sponsor shall submit such additional reports concerning the effect as FDA requests

8.4.3 Unanticipated Problem Reporting

Incidents or events that meet the OHRP criteria for UPs require the creation and completion of an UP report form. It is the site investigator's responsibility to report UPs to their IRB and to the DCC/study sponsor. The UP report will include the following information:

- Protocol identifying information: protocol title and number, PI's name, and the IRB project number;
- A detailed description of the event, incident, experience, or outcome;

CONFIDENTIAL

This material is the property of the NYU School of Medicine and Langone Medical Center. Do not disclose or use except as authorized in writing by the study sponsor
Interventional Template Version: 12 February 2020

- An explanation of the basis for determining that the event, incident, experience, or outcome represents an UP;
- A description of any changes to the protocol or other corrective actions that have been taken or are proposed in response to the UP.

To satisfy the requirement for prompt reporting, UPs will be reported using the following timeline:

- UPs that are SAEs will be reported to the IRB and to the DCC/study sponsor within 5 **working days** of the investigator becoming aware of the event.
- Any other UP will be reported to the IRB and to the DCC/study sponsor within 10 working days of the investigator becoming aware of the problem.

8.4.4 Reporting of Pregnancy

If the subject participating in the study is found to be pregnant during the study period, participant will immediately be withdrawn from the study and IRB will be informed.

8.5 Reporting Procedures – Notifying the Study Sponsor

The study clinician will complete a SAE Form within the following timelines:

- All deaths and immediately life-threatening events, whether related or unrelated, will be recorded on the SAE Form and submitted to the study sponsor (PI) within 24 hours of awareness.
- Other SAEs regardless of relationship will be submitted to the study sponsor (PI) within 72 hours of site awareness.

All SAEs will be followed until satisfactory resolution or until the site investigator deems the event to be chronic or stable. Other supporting documentation of the event may be requested by the study sponsor and should be provided as soon as possible.

As a follow-up to the initial report, within the following 48 hours of awareness of the event, the investigator shall provide further information, as applicable, on the unanticipated event or the unanticipated problem in the form of a written narrative. This should include a copy of the completed Unanticipated Problem form, and any other diagnostic information that will assist the understanding of the event. Significant new information on ongoing unanticipated adverse effects shall be provided promptly to the study sponsor.

8.6 Reporting Procedures – Notifying the FDA

The study sponsor is required to report certain study events in an expedited fashion to the FDA. These written notifications of adverse events are referred to as IDE safety reports.

- ***Within 10 working days (via telephone or facsimile report)***
Any study event that is:
 - associated with the use of the study device, and
 - unanticipated,regardless of the seriousness of the event.

CONFIDENTIAL

- ***Within 5 working days (via written report)***
 - Protocol deviation to protect the life of the subject in emergency
 - Withdrawal of IRB approval
 - Lack of informed consent

Additional reporting requirements

Sponsors are also required to identify in IDE safety reports all previous reports concerning similar adverse events and to analyze the significance of the current event in light of the previous reports.

Reporting Process

Adverse events may be submitted on FDA Form 3500A (MEDWATCH Form) [attachment 9], or in a narrative format.

8.7 Safety Oversight

It is the responsibility of the Principal Investigator to oversee the safety of the study. This safety monitoring will include careful assessment and appropriate reporting of adverse events as noted above, as well as the construction and implementation of a site data and safety-monitoring plan. Medical monitoring will include a regular assessment of the number and type of serious adverse events. Data (demographics, eligibility criteria), screening methods, and adverse events will be assessed by the PI who is a fellowship trained interventional radiologist and licensed physician monthly to ensure study safety, compliance, and integrity/accuracy of data in accordance with the data safety monitoring plan.

Administration of study procedure will be halted when three moderate or higher grade AEs determined to be “related” are reported to the sponsor (PI). The PI will notify the study investigators immediately when the third grade 3 event is reported and enrollment screens will stop accepting new study participants. The study sponsor will convene a meeting with study investigators by teleconference or in writing as soon as possible and will provide recommendations for proceeding with the study. The study sponsor will inform the IRB and FDA of the temporary halt and the disposition of the study.

The outcomes of these reviews, when adverse events are captured will be communicated directly with the IRB. A summary of these reviews will be submitted to the IRB as part of an annual progress report at Continuing Review.

Specific data safety monitoring plan is listed below:

- 1- Vascular injury / non-target embolization to lower extremity, bleeding, access site complications will be monitored as follows:
 - a. On the day of procedure, interventional radiologist (investigator) performing the procedure will assess access site and lower extremity pulses and document
 - b. Day 1 visit / telemedicine visit: investigator will assess for symptoms in the target lower extremity (pain, swelling at access site and document findings
 - c. 4 weeks follow up visit: investigator will assess groin access site for hematoma, pseudoaneurysm and assess lower extremity pulses
- Skin ulceration, cutaneous purpura, plantar or peripheral sensory paresthesia will be monitored as follows:
 - Each follow up visit, an investigator will assess for symptoms and signs in the target lower extremity and document

CONFIDENTIAL

9 Clinical Monitoring/Quality Assurance

Clinical site monitoring is conducted to ensure that the rights and well-being of human subjects are protected, that the reported trial data are accurate, complete, and verifiable, and that the conduct of the trial is in compliance with the currently approved protocol/amendment(s), with GCP, and with applicable regulatory requirement(s).

- Monitoring for this study will be performed by the study PI once every 3 months.
- Monitoring activities include communication with the sub-investigators and study site staff; review of the study site's processes, procedures, and records; and verification of the accuracy of data.

10 Statistical Considerations

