8.1.3 Definition of Unanticipated Problems (UP)

Unanticipated Problems Involving Risk to Subjects or Others

Any incident, experience, or outcome that meets all of the following criteria:

- Unexpected in nature, severity, or frequency (i.e. not described in study-related documents such as the IRB-approved protocol or consent form, the investigators brochure, etc)
- Related or possibly related to participation in the research (i.e. possibly related means there is a reasonable possibility that the incident experience, or outcome may have been caused by the procedures involved in the research)
- Suggests that the research places subjects or others at greater risk of harm (including physical, psychological, economic, or social harm).

CONFIDENTIAL

Unanticipated adverse device effect, any serious adverse effect on health or safety or any life-threatening problem or death caused by, or associated with, a device, if that effect, problem, or death was not previously identified in nature, severity, or degree of incidence in the investigational plan or application, or any other unanticipated serious problem associated with a device that relates to the rights, safety, or welfare of subjects (21 CFR 812.3(s)).

8.2 *Classification of an Adverse Event*

8.2.1 **Severity of Event**

The Investigator will assess the severity (intensity) of each adverse event as mild, moderate, severe, life-threatening / disabling event, or death/ unexpected pregnancy abortion. The investigator will also categorize each adverse event as to its potential relationship to study drug using the categories of yes or no.

The severity and causality of all adverse events will be graded according to the new adverse event classification by the Society of Interventional Radiology Standards of Practice Committee [30], as follows:

- **Mild AE:** No therapy or nominal (non-substantial) therapy (postprocedural imaging performed and fails to show manifestation of AE); near miss (eg, wrong site of patient prepared, recognized and corrected before procedure, wrong patient information entered for procedure);
- **Moderate AE:** moderate escalation of care, requiring substantial treatment, eg, intervention (description of intervention and result of intervention) under conscious sedation, blood product administration, extremely prolonged outpatient observation, or overnight admission after outpatient procedure not typical for the procedure (excludes admission or hospital days unrelated to AE);

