- **Severe AE:** marked escalation of care, ie, hospital admission or prolongation of existing hospital admission for > 24 hours, hospital admission that is atypical for the procedure, inpatient transfer from regular floor/telemetry to intensive care unit, or complex intervention performed requiring general anesthesia in previously non-intubated patient (generally excludes pediatrics or in circumstances in which general anesthesia would primarily be used in lieu of conscious sedation, eg, in mentally challenged or severely uncooperative patients);
- **Life-threatening or disabling event:** eg, cardiopulmonary arrest, shock, organ failure, unanticipated dialysis, paralysis, loss of limb or organ;
- **Patient death or unexpected pregnancy abortion.**

For AEs not included in the protocol defined grading system, the following guidelines will be used to describe severity.

- **Mild** – Events require minimal or no treatment and do not interfere with the participant's daily activities.
- **Moderate** – Events result in a low level of inconvenience or concern with the therapeutic measures. Moderate events may cause some interference with functioning.
- **Severe** – Events interrupt a participant's usual daily activity and may require systemic drug therapy or other treatment. Severe events are usually potentially life-threatening or incapacitating.

8.2.2 **Relationship to Study Device**

CONFIDENTIAL

For all collected AEs, the clinician who examines and evaluates the participant will determine the AE's causality based on temporal relationship and his/her clinical judgment. The degree of certainty about causality will be graded using the categories below according to the new adverse event classification by the Society of Interventional Radiology Standards of Practice Committee

- Category 1: AE not caused by procedure. The AE is completely independent of study drug administration, and/or evidence exists that the event is definitely related to another etiology. There must be an alternative, definitive etiology documented by the clinician.
- Category 2: Unknown whether AE was caused by the procedure.
- Category 3: AE caused by the procedure. There is clear evidence to suggest a causal relationship, and other possible contributing factors can be ruled out.

The definition implies a reasonable possibility of a causal relationship between the event and the study device. This means that there are facts (evidence) or arguments to suggest a causal relationship.

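### The safety halting rule in Section 8.7 gives two inconsistent triggers in consecutive sentences, uses an undefined grade, and does not say which causality classification defines a related event

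*Combined protocol and SAP*

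**What the plan says.** Section 8.7 (Safety Oversight) contains the halting rule. Its first sentence reads "Administration of study procedure will be halted when three moderate or higher grade AEs determined to be" related, as reported to the sponsor, who is the PI. The next sentence reads "The PI will notify the study investigators immediately when the third grade 3 event is reported and enrollment screens will stop accepting new study participants". After that, Section 8.7 describes a meeting of the study investigators and notice of the temporary halt to the IRB and FDA.

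Severity is defined in Section 8.2.1, where the investigator grades each event "as mild, moderate, severe, life-threatening / disabling event, or death/ unexpected pregnancy abortion". The levels have names and descriptions but no numbers. The third named level, severe, is described as "marked escalation of care, ie, hospital admission or prolongation of existing hospital admission for > 24 hours", among other criteria. For events outside that system, the same section adds a fallback mild/moderate/severe scale with different descriptions, also unnumbered.

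Causality appears twice. Section 8.2.1 has the investigator record "its potential relationship to study drug using the categories of yes or no". Section 8.2.2 uses three categories: "Category 1: AE not caused by procedure", then "Category 2: Unknown whether AE was caused by the procedure", then a Category 3 for events caused by the procedure. Category 1 requires a documented, definitive alternative cause. Category 3 requires clear evidence, with other contributing factors ruled out.

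**The concern.** A halting rule has to give the same answer to anyone who applies it to the same events. This one does not. The two sentences differ in three respects: the severity that counts, whether relatedness is required, and the action that follows. The grade number in the second has no counterpart in the severity scale, and the word related in the first is not tied to either causality classification.

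The stakes come from the rule's position in the safety plan. Section 5.8 lists general grounds for suspension, such as unacceptable risk, but gives no count, so Section 8.7 holds the only numeric trigger. The person who applies it is the PI, who is also the sponsor receiving the reports (Sections 8.5 and 8.7) and one of the two operators (Section 1). Any ambiguity would be settled during the trial, with the events already known, by someone who performs the procedure.

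**Working it through.** **Step 1. The two triggers side by side (Section 8.7).**

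| | First sentence | Second sentence |
|---|---|---|
| Count | three | third |
| Severity | moderate or higher | 'grade 3' |
| Relatedness | required | not mentioned |
| Action | procedure halted | investigators notified, enrolment stopped |

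**Step 2. What grade 3 could mean.** By position in Section 8.2.1 the levels are 1 mild, 2 moderate, 3 severe, 4 life-threatening or disabling, 5 death or unexpected pregnancy abortion. On that count grade 3 is severe. The numbering is the reader's; the protocol supplies none.

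**Step 3. Apply both sentences to the same events, taking grade 3 as severe.**

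| Events reported | Procedure halt | Notification and enrolment stop |
|---|---|---|
| Three moderate, related | yes | no |
| Three severe, related | yes | yes |
| Three severe, unrelated | no | yes, as written |

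The sentences agree in the second row and conflict in the other two.

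**Step 4. What related could mean.** There are at least three candidates: a yes on the 8.2.1 item (worded for a study drug, in a device trial), Category 3 only, or Categories 2 and 3 together. Section 8.2.2 also remarks, after listing the categories, that the definition implies a reasonable possibility of a causal link. That is a looser standard than the wording of Category 3. Section 8.7 refers to none of these, so the status of Category 2 is open.

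**Step 5. Does it matter which events count?** The protocol states no operating characteristic for the rule, so there is no figure to reproduce. It also gives no expected event rate on the 8.2.1 scale. The background section reports moderate puncture-site haemorrhage in 12 of 72 and 1 of 14 patients in two earlier studies, but those events were not graded on this scale and are not used as inputs.

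For illustration only, take n = 50 (planned accrual, Section 5.6), an assumed per-patient rate p of qualifying events, and at most one qualifying event per patient:

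P(at least 3) = 1 − [(1−p)^50 + 50·p·(1−p)^49 + 1225·p²·(1−p)^48]

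At p = 0.05 this is 1 − (0.0769 + 0.2025 + 0.2611) = 0.4595.

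| Assumed rate p | 1% | 2% | 3% | 5% | 10% |
|---|---|---|---|---|---|
| P(at least 3 among 50) | 1.4% | 7.8% | 19% | 46% | 89% |

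Over this range the chance of reaching three moves from remote to likely. Adding or removing a severity level, or the events of unknown cause, changes p and so changes how the rule behaves.

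**The case against.** The best defence is that the second sentence merely carries out the first: grade 3 is loose drafting for the third qualifying event, and one trigger was intended. That may be the intent, but the text does not say so. The defence still requires choosing between the two severity descriptions and deciding whether relatedness applies.

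Several stronger readings are tempting and should be resisted.

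- *Moderate events would never trigger a halt.* Not so. The first sentence governs the procedure and expressly covers moderate events. Three related moderate events stop treatment; what is left open is notification and enrolment.
- *The protocol has no way at all to call an event related.* The yes/no item in 8.2.1 could serve. The defect is that two classifications exist and the rule names neither.
- *Most events will be classed as unknown.* The strict wording of Categories 1 and 3 makes this plausible, but the documents contain no data on it. What is established is that the status of such events is unspecified.
- *The count of three was carried over when planned enrolment rose from 29 to 50.* Section 10.5 gives the earlier sample size, but the earlier halting text is not in the documents. A fixed count that makes a temporary pause more likely in a larger study is also a design trade-off, not an error.
- *The two triggers differ by a known factor, for example 46% against 1.4%.* That contrast comes entirely from assuming 5% for one trigger and 1% for the other. The second sentence, as written, also counts unrelated events, so a low rate for it is not evident.

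It is also fair to say that other safeguards exist: suspension for unacceptable risk (5.8), monthly PI review (8.7), and reporting of unanticipated device effects (8.4.2 and 8.6). These limit the harm but do not make the numeric rule determinate.

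**Conclusion.** The point stands as a contradiction within Section 8.7 and between it and Sections 8.2.1 and 8.2.2. Followed literally, the only numeric halting trigger gives conflicting actions for the same events, and nothing elsewhere in the protocol resolves it. It should be corrected before the rule is relied on.

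This conclusion rests on the text alone. Taking grade 3 to mean severe is an assumption, needed only for the worked scenarios; without it the term is simply undefined. The probabilities of 1.4% to 89% show sensitivity to what is counted and are not estimates for this trial. They assume independent patients and at most one qualifying event each, whereas the rule counts events. They describe reaching three among all 50, which is not strictly the chance of a halt, because an event after the last treatment cannot halt treatment.

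**What to change.** Reconcile Sections 8.2.1, 8.2.2 and 8.7 so that:

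1. every severity threshold in 8.7 uses a level defined in 8.2.1, with no undefined grade numbers;
2. each of the three actions (procedure halt, notification, enrolment stop) has its own unambiguous trigger, including whether relatedness is required;
3. one causality scale is used throughout, worded for the device or procedure, with an explicit statement of which categories count towards the rule, including Category 2.

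Which thresholds and categories to adopt, and whether the actions share a trigger, is for the sponsor's clinicians, the IRB and FDA. The cost is a short text amendment, with IRB approval before it takes effect (Section 13.2). It needs no added data or staff.

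### Section 8.7 halts the procedure at three related AEs of moderate or higher grade, but ties the notification and enrolment stop to a third grade 3 event, a grade that 8.2.1 does not define

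*Combined protocol and SAP*

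**What the plan says.** Section 8.7 begins the rule this way: "Administration of study procedure will be halted when three moderate or higher grade AEs", judged related, have been reported to the sponsor, who is the PI. The sentence directly after it says that the PI will "notify the study investigators immediately when the third grade 3 event is reported and enrollment screens will stop accepting new study participants". Two follow-up steps come next. One is a review: "The study sponsor will convene a meeting with study investigators by teleconference or in writing as soon as possible". The other is outside notice: "The study sponsor will inform the IRB and FDA of the temporary halt".

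The severity terms come from 8.2.1. It has all AEs graded on the Society of Interventional Radiology (SIR) classification, given as five named levels: mild, moderate, severe, life-threatening or disabling, and death or unexpected pregnancy abortion. SIR Mild means "No therapy or nominal (non-substantial) therapy". SIR Moderate means substantial treatment, with examples that include "blood product administration, extremely prolonged outpatient observation, or overnight admission after outpatient procedure not typical for the procedure". A second list of mild, moderate and severe then follows: "For AEs not included in the protocol defined grading system, the following guidelines will be used to describe severity". On that second list, "Moderate events may cause some interference with functioning".

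Relatedness also appears in two forms. Section 8.2.1 asks for yes or no. Section 8.2.2 asks for one of three categories: not caused by the procedure (1), unknown (2), caused by the procedure (3).

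**The concern.** A halting rule should let anyone holding the AE log say, without interpretation, whether it has been met. Here two adjacent sentences describe what looks like a single event, the third qualifying AE, in different terms. The first uses a level that 8.2.1 defines. The second uses a number that the protocol does not define for AEs, and it drops both the reference to relatedness and the words that extend the threshold upward.

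At stake is what happens after three related Moderate AEs. If grade 3 means Severe, the procedure is on hold, yet the text requires neither an immediate message to the investigators nor an end to enrolment. People could still sign consent and go through baseline procedures for an intervention that they cannot receive for the time being.

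The wording matters more here because the PI holds several roles: one of the two operators (Section 1), the sponsor to whom SAEs are reported (8.5), the monthly safety reviewer (8.7) and the quarterly monitor (Section 9). The person who applies the rule should not also have to decide what it means.

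**Working it through.** The protocol gives no operating characteristic for the halting rule, so there is no figure to reproduce. The check is a comparison of texts.

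**Step 1. The two sentences of 8.7 side by side.**

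| Element | First sentence | Second sentence |
|---|---|---|
| Count | three AEs | the third event |
| Severity | moderate or higher | grade 3, with no upward extension |
| Relatedness | required | not mentioned |
| Action | procedure halted | investigators told at once; enrolment stopped |

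**Step 2. What grade 3 could mean.** Neither severity list in 8.2.1 is numbered. The only numbered AE scale in Section 8 is the causality scale of 8.2.2, which is not a severity grade. Grade 3 elsewhere in the document is a radiographic osteoarthritis grade. The natural guess is list position: Mild = 1, Moderate = 2, Severe = 3. Severe is third in both the five-level SIR list and the three-level fallback list. The first sentence starts at position 2 and the second at position 3, so the thresholds differ by 3 − 2 = 1 level.

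**Step 3. Test cases, taking grade 3 as Severe.** Each row assumes that these three AEs are the only ones above Mild.

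| Three AEs on record | Procedure halt | Notification and enrolment stop |
|---|---|---|
| Moderate, related | met | not met |
| Severe, related | met | met |
| Severe, unrelated | not met | met as written; not met if relatedness is implied |
| Life-threatening, related | met | not met as written; met if higher grades are implied |

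The first row is the defect, and it holds whether or not the missing qualifiers are read into the second sentence. The last two rows show that any broader statement about how the triggers relate depends on which qualifiers are supplied.

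**Step 4. What still happens in the first row.** The procedure is halted, the sponsor convenes the investigators as soon as possible, and the IRB and FDA are informed. What remains open is the flow of new participants: consent and screening (7.3.1), then baseline questionnaires, examination, blood and urine samples, and an MRI or radiograph where no recent one exists (7.3.2). Section 7.3.3 places the intervention within 30 days of visit 1, so a hold could outlast that window for someone screened during it.

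**Step 5. Does a single severity threshold settle the count?** Not fully. Take two Moderate AEs in Category 3 and one in Category 2. If Category 2 does not count as related, the total is 2 and nothing halts. If it does, the total is 2 + 1 = 3 and the procedure halts. Section 8.7 does not say which applies, and the yes/no scale in 8.2.1 is not mapped to the three categories.

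**Step 6. Which severity list feeds the count?** An untreated AE that limits function is Mild on SIR and would not count. On the fallback list it could be called Moderate and would count. Because 8.2.1 assigns SIR to all AEs, and 10.4.4 repeats this, SIR is the better reading, but 8.7 does not say so.

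**The case against.** The strongest reply is that this is leftover wording. Section 8.7 runs as one sequence: three AEs, the third event, a meeting, then a temporary halt in the singular. The table of contents lists a separate halting-rules heading that the body no longer has, which fits merged text. One trigger was very probably intended. That stands as an account of intent, but it does not settle the rule: the sentences could be reconciled at Moderate or at Severe, and the protocol does not choose.

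The second reply is that the protective act already sits at the lower threshold and in defined terms. That also stands, and it rules out two stronger inferences. A reader might conclude that more participants could be embolized after the third related Moderate AE; the first sentence forbids it on either reading. A reader might also conclude that the second operator could carry on unaware; a halt at a single centre with two operators binds both and can hardly be carried out without telling the other one.

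Third, the fallback severity list may have a use. Several SIR levels are framed around a procedure, while AEs here include intercurrent illness. Misapplying the list would tend to bring the halt forward. No harm from keeping it has been shown, so this point gives no reason to delete it.

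**Conclusion.** The inconsistency is real and concerns a safety threshold. Taking grade 3 as the third level counted up from Mild, three related Moderate AEs halt the procedure without requiring the immediate notification or the enrolment stop. The practical effect is limited mainly to continued consent, screening and baseline visits during a hold. It should be corrected, mainly because correction is so cheap.

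No probability is given. The documents contain no related-AE rates by SIR grade, and the complications reported from earlier studies in 2.2.2 are not graded that way.

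A reader might go further and say that the two triggers meet only when all three AEs are Severe or higher, that the enrolment stop might therefore never operate, or that deaths are excluded from it. The documents do not support these as general statements. The first two need both relatedness and an upward extension to be carried into the second sentence. The third needs the upward extension to be left out. If relatedness is not required, unrelated Severe AEs also count, and the enrolment stop could come at the same event as the halt, or before it.

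The documents do not show whether enrolment is still open. If it has closed, the amendment does little prospectively, but the recount still shows whether a halt and its notifications were due.

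**What to change.** In 8.7:

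- Replace the reference to a third grade 3 event with *the third related AE of SIR grade moderate or higher*. This is the threshold already set for the procedure halt, in terms that 8.2.1 defines.
- State that this one trigger governs the procedure halt, the investigator notification and the enrolment stop.
- State that the SIR grade determines the halting count. The fallback list in 8.2.1 can then stay as it is.
- State which causality category or categories in 8.2.2 count as related, and in particular whether Category 2 does. Including it can only bring the halt forward.

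Then recount the AEs recorded so far against that trigger.

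The cost is a wording amendment with IRB approval, which 13.2 requires before a change is implemented, and one pass through AE forms already completed. No new data or staff are needed. One consequence should be accepted openly: AEs that limit function but need no substantial treatment will not count toward the halt, as is already so under SIR. They remain recorded and visible at the PI's monthly review.
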